Compensation for Peer Leader participants. Peers will be compensated for their time and travel and incentivized to actively participate in each visit by providing a ClinCard up to a total of \$425 over the course of the study for 9 visits. Peer Leaders will receive the incentive by having it added to a debit card, after attending each visit. The payments will occur as follows: Visit 1: \$30, Visit 2: \$40, Visits 3-4: \$45 each, Visits 5-7: \$50 each, Visit 8: \$55, Visit 9: \$60. Peers will not receive any compensation for visits in which they do not attend. Additionally, Peer Leaders may be able to receive an additional \$60 for each of two optional follow-up visits after the completion of intervention (up to two more visits).

Training in Ethical Conduct of Research for Peer Leaders: Although we will be collecting data from the Peers in order to evaluate the study and the Peers are also research subjects in this study, as part of the overall intervention, Peers will be conducting online recruitment and outreach and therefore we will make sure that Peers have a clear understanding of their roles in this capacity. We will initially conduct a two-session training with the Peers where they will go through our community research ethics training. I adapted this training from a World Health Organization training manual for lay community members, such as our Peers, participating as 'community researchers' to make accessible to them training in research ethics. It covers topics in history of research ethics, privacy and confidentiality, vulnerable subjects, ethical recruitment practices, protecting against risks, minimizing risks, and personal safety and conduct. This training has previously used with community partners for whom the CITI course is inaccessible due to literacy and/or language barriers. Additionally, we will have ongoing trainings throughout the project period in online privacy, security issues, and confidentiality with information. Peers in the study are not key personal, however we believe it is important that they do understand research ethics.

PROCEDURES FOR GENERAL PARTICIPANTS

Recruitment:

1. We will first randomize the 16 to 20 peers, 1:1 to either E-PrEP or BxNow (control condition).
2. Peers will then recruit n=240 participants total from their personal online social networks to their assigned condition (E-PrEP or BxNow). On average, each peer will recruit approximately 15 participants each.

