3. **Peers will actively recruit online** within their pre-existing social networks using text messages, brief videos, and picture graphics, using whichever mode is deemed appropriate. These recruitment advertisements will be co-developed by the Peers and investigators. Peers will then post the designated messages to their online social networks.
4. **In addition to recruitment lead by peers**, the research team will use the a study Facebook profile to buy ads on Facebook to outreach to potential participants. The ads will be targeted to 18-29 year old men who live in New York City, who are interested in Men, Men and Women or Unspecified, and who identify as Latino, Hispanic, Black or African American. Examples of the Facebook Ads can be found in the Participant Recruitment File. We will assign participants randomly with equal number to the Facebook groups of Peers Leaders who are having trouble with recruitment.
5. All recruitment messages will have customized links (enabling tracking of recruitment method and online venue) that will then lead participants to a secure study information and screening page (which will be cross-compatible across devices, e.g. a computer, iPad, or other mobile device such as smart-phones). To prevent inappropriate participants from joining the study and not inadvertently discourage appropriate participants, we will not display specific eligibility requirement on the recruitment messages.
6. Due to technological advancements, the ads will be geographically limited to those potential participants accessing these sites from the New York or have indicated a New York address on their social media profile. We have used this approach in our recently completed *theSEXword* social media pilot. While we will not explicitly exclude individuals not living or working in the Bronx, the above methods will help limit issues with potential participants being accidentally excluded and inappropriately included. This will also help reduce the burden of questions participants need to answer in the screening page. This approach will enable us to obtain a diverse sample of YMCSM living or working in

the New York.

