Compensation: Participants will be given \$20, \$30, and \$40 and \$20 as incentives after completion of assessments at baseline (T1), 6 weeks (T2), and 12 weeks(T3), and post 36 weeks (T4) (respectively). The participants will be given the choice to receive their incentives either via e-codes, Amazon online-gift cards, or by receiving a Clincard.

Data Collection:

We will collect three general types of data: 1) online processes (e.g. referral source, # of platforms joined by each participant); 2) measures of engagement with intervention components (e.g. # of views, time spent online); and 3) measures of outcome and independent variables, collected through online surveys at the ~~four~~three time points (see Table 2). To help assess both degree of exposure to intervention components and possible contamination between the two conditions, the surveys at 6 weeks (T2), ~~and~~ 12 weeks (T3) will display random samples of study and non-study graphics and posts and ask participants if they recall seeing them, with E-PrEP materials embedded in the choices.^{106,119,141}

Table 2. Data Collection					
Measures	Week	0	6	12	36+
PrEP intention, use, knowledge, attitudes		x	x	x	x
Perceived PrEP attributes		x	x	x	
HIV testing, risk behaviors		x	x	x	
Peer affinity and network data		x	x	x	

Table 2. Data Collection					
Measures	Week	0	6	12	36+
PrEP intention, use, knowledge, attitudes		x	x	x	x
Perceived PrEP attributes		x	x	x	
HIV testing, risk behaviors		x	x	x	
Peer affinity and network data		x	x	x	
Sociodemographic Factors		x			
Sexual Orientation		x			
Healthcare access		x	x	x	
Substance use		x	x	x	
Perceived risk, stigma		x	x	x	
Social media engagement		x	x		
Intervention exposure			x	x	

Data Security:

In order to securing information over the Internet and social media, and protecting participant data, an electronic, password protected and encrypted system will be developed to store analyses, and social media activity will remain private to study participants.¹⁶⁴ Research participants will be informed of how communications are recorded and stored during the online informed consent process. Due to the ever-changing and evolving nature of privacy issues on social media sites, we will review privacy settings for all social media study sites at least every four weeks and adjustments will be made to the study sites as necessary.

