1. <https://www.qualtrics.com/support/survey-platform/survey-module/survey-options/survey-protection/#PreventingRespondentsFromTakingYourSurveyMoreThanOnce>

Furthermore, we will download the raw data and store it in a password protected *and* encrypted file on the office computer of [name]. Only the PIs and research study staff will have access to the full data-set.

Analytic Plan: Our *primary outcome* will be *intention to use PrEP*,⁸³ which we consider a predictor of subsequent use,¹⁴² and will be measured using a Likert scale. We will use ‘intention’ as a proxy given the low likelihood of actual PrEP use.^{83,132,143} *Secondary outcomes* will be PrEP use, knowledge,¹⁴³ perceptions about PrEP¹³⁴ and HIV testing- and risk-behaviors.¹⁴⁴ *Covariates*^{80,81,143,145-148} will include access to medical care (including HIV/STI testing), sexual orientation, HIV and PrEP related stigma, substance use, sociodemographic factors,¹⁴⁴ social media engagement and network data,^{149,169} and perceived affinity to the referring Peer.¹⁵⁰ First, we will compare groups for equivalence at baseline, using chi-square or t-tests as appropriate. In addition, we will determine whether subgroups (e.g., grouped by number of social media sites joined, social media platform(s) used, peer referent, race/ethnicity, and sexual orientation) differ with respect to the primary and secondary outcomes. Relevant differences will be used as covariates in subsequent models. At each time point, we will examine change in our primary outcome variable (*intention to use PrEP*) by using a traditional two-sample test of proportions. To compare differences in outcomes between arms over time, we will use

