repeated measures mixed-effects logistic and linear models, with the treatment arm as a fixed-effect, Peers as a random-effect, and time (as a linear term) as an independent variable. We will also look at residual plots to determine if we need to include non-linear terms for time. Next, we will use hierarchical models to examine the role of secondary outcomes as potential mediators of change over time, e.g. are there differences by condition in PrEP knowledge or perceptions that account for differences in intentions. Finally, we will assess the impact of the exposure arm (E-PrEP or BxNow) and selected covariates (significant in the bivariate analysis at $p < 0.1$) on the primary and secondary outcomes using mixed-effects models. We will also assess the impact of online process and engagement variables on outcomes. To overcome possible limitations due to intra-cluster correlations, we will include a modified sensitivity analysis that examines outcomes in relation to participants' network size and perceived affinity to the Peers. To test *feasibility*, we will assess online process measures, including participation rate (# of individuals screening eligible and then ultimately joining the study), engagement activity (e.g. time spent viewing posted videos, # of responses posted to questions, participation in polls, etc.), and retention (# of participants actively 'leaving' or 'un-joining' a social media study site and # of respondents to follow-up assessments).

Power Analysis: The primary purpose of this study is to test feasibility and to obtain an effect size estimate for a future R01 application. We estimate that a sample size of 220, accounting for up to 20% attrition¹⁰⁶ will provide 80% power to detect an effect size of 20% in E-PrEP vs. 5% in BxNow in the proportion of participants indicating '*intention to use PrEP*' at 6 weeks, with a two-sided $\alpha < .05$. We will also have adequate power to detect a smaller effect size at 12 weeks because of our repeated measures design. This conservative effect size estimate is reasonable, given the novelty of the proposed intervention, the absence of other studies assessing uptake of a biomedical tool in YMSM, and the results of other studies assessing potential interest in PrEP.⁸³

Procedures outlined below have been guided by [name] (Consultant), and by [name] (Consultant), who has extensive experience in conducting online survey and intervention studies with vulnerable populations including MSM.

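### The 80% power claim states no allowance for clustering by Peer and, at 20% attrition, holds only up to an ICC of 0 to about 0.03; the 12-week power claim has no calculation behind it

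*Combined protocol and SAP*

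**What the plan says.** The Power Analysis reads: "We estimate that a sample size of 220, accounting for up to 20% attrition" "will provide 80% power to detect an effect size of 20% in E-PrEP vs. 5% in BxNow", at 6 weeks, two-sided at the 5% level. It continues: "We will also have adequate power to detect a smaller effect size at 12 weeks because of our repeated measures design". The same paragraph describes the study's main purpose as feasibility and an effect size estimate for a later grant application.

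The design is set out elsewhere. Peers are randomised 1:1, numbering 16 to 20 in Methods (Participants) and in the Recruitment steps for general participants, and 16 in section I.1.2. Planned enrolment is 240, 120 per arm, at about 15 per Peer. Some participants recruited through advertisements are placed differently: "We will assign participants randomly with equal number to the Facebook groups of Peers Leaders who are having trouble with recruitment".

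The Analytic Plan tests the primary outcome at each time point "by using a traditional two-sample test of proportions" and adds longitudinal mixed models with a random effect for Peer. It also anticipates correlation within Peers: "To overcome possible limitations due to intra-cluster correlations, we will include a modified sensitivity analysis that examines outcomes" by network size and affinity to the Peer.

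**The concern.** In a cluster-randomised trial, participants attached to the same Peer carry less information than the same number of independent people. There is good reason to expect some correlation here: most participants come from a Peer's own online network, and under Anticipated components of E-PrEP each Peer words the posts personally. The Analytic Plan recognises this, but the Power Analysis does not mention it. If no allowance was made, the stated 80% belongs to an individually randomised trial of the same size.

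The 12-week sentence claims still more, power for a smaller effect, and gives nothing by which to check it. At stake is whether a reader, or the planners of the later trial, can rely on the stated power. The conduct of this study is not threatened.

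**Working it through.** **Inputs.** From the Power Analysis: 20% vs 5%, two-sided 0.05, 80% power, 220 enrolled, 20% attrition. From Methods: 240 enrolled, 16 to 20 Peers. The ICC is not given; 0.01 to 0.10 is assumed, with equal numbers per Peer.

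**Reproducing 220.** Without continuity correction, with mean proportion 0.125:

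n = [1.960·√(2·0.125·0.875) + 0.842·√(0.20·0.80 + 0.05·0.95)]² / 0.15² = 75.12, so 76 per arm, and 2·76/0.8 = 190.

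With continuity correction:

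n = (75.12/4)·[1 + √(1 + 4/(75.12·0.15))]² = 87.95, so 88 per arm, and 2·88/0.8 = 220.

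The corrected formula matches exactly with a design effect of 1. This is strong evidence but not proof. An uncorrected calculation with an unstated design effect of 220/190 = 1.158 would also give 220; at 15 per Peer that is an ICC of 0.158/14 = 0.011. On either route, no allowance is stated.

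**Largest ICC that keeps 80% power.** Let R be the number retained, K the number of Peers and m = R/K. The effective number per arm is (R/2)/(1 + (m − 1)·ICC). For the z formulas the ceiling is (R/2 ÷ required n − 1)/(m − 1). For example, with 240 enrolled, 20% attrition and 16 Peers, R/2 = 96 and m = 12, so the uncorrected ceiling is (96/75.12 − 1)/11 = 0.025. The t rows use a non-central t on K − 2 degrees of freedom with unpooled variance, solved numerically.

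| 20% attrition | 220, 16 Peers | 220, 20 Peers | 240, 16 Peers | 240, 20 Peers |
|---|---|---|---|---|
| Ceiling, corrected z | 0 | 0 | 0.008 | 0.011 |
| Ceiling, t | 0.005 | 0.011 | 0.013 | 0.022 |
| Ceiling, uncorrected z | 0.017 | 0.022 | 0.025 | 0.032 |
| Power at ICC 0.05, corrected z | 58.8% | 63.0% | 61.8% | 66.2% |
| Power at ICC 0.05, t | 65.1% | 69.8% | 67.4% | 72.3% |
| Power at ICC 0.05, uncorrected z | 69.5% | 72.8% | 71.9% | 75.4% |

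**Planned design.** With 240 enrolled and 20% attrition (96 per arm):

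| ICC (assumed) | Design effect, 16 / 20 Peers | Power by t, 16 / 20 Peers | Simulated power, 16 / 20 Peers |
|---|---|---|---|
| 0.01 | 1.11 / 1.09 | 81.2% / 83.3% | 82.5% / 84.9% |
| 0.02 | 1.22 / 1.17 | 77.5% / 80.5% | 79.0% / 81.7% |
| 0.05 | 1.55 / 1.43 | 67.4% / 72.3% | 69.7% / 74.5% |
| 0.10 | 2.10 / 1.86 | 54.5% / 61.0% | 57.1% / 63.6% |

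The simulation used beta-binomial Peers and a Peer-level t-test, with 40,000 runs. It lies 1 to 3 points above the formula throughout.

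**Less attrition.** With 240 enrolled and uncorrected z, the ceiling rises to 0.035 / 0.045 (16 / 20 Peers) at 10% attrition and 0.043 / 0.054 with none. At ICC 0.05, over all the cases, power is 63% to 79% at 10% attrition and 66% to 81% with none. Only one case passes 80%: 240 enrolled, 20 Peers, no attrition, uncorrected.

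**12 weeks.** The plan gives no effect size, within-person correlation, ICC, model or power figure, so there is nothing to recompute. Table 2 (Data Collection) schedules "PrEP intention, use, knowledge, attitudes" at baseline, 6, 12 and 36+ weeks. Those repeated values may sharpen the longitudinal model, but a two-sample test at a single time point gains nothing from them.

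**The case against.** The strongest reply is that nothing in the stated arithmetic is wrong: 220 can be reproduced, and the shortfall rests entirely on ICC values that no document supplies. That is correct. The defect is an unstated assumption, and the power is roughly met at an ICC of 0.01 to 0.02. Standardised content, and advertisement recruits placed at random with some Peers, may pull the ICC down, though by an unknown amount.

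The zero ceiling applies to 220 enrolled under the corrected formula. The plan enrols 240, where the ceiling is never zero, and the Analytic Plan mentions no continuity correction. Other formulas move the upper end too: for 240 and 20 Peers, unpooled z gives 0.038 and arcsine 0.045, though neither reproduces 220. A pooled-variance t gives only 0.001 to 0.016 across the four designs. None of this changes the picture at 0.05, where every tabulated case at 20% attrition is below 80%.

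The 12-week sentence appeals to the repeated-measures model rather than the single-time-point test, so that test alone does not refute it. The sentence is still unquantified. The Peer random effect handles clustering in the longitudinal inference but does not restore the stated power.

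Finally, this is a feasibility study and no stated decision depends on 80% power. That limits the consequence, but the plan does assert 80% for a cluster-randomised comparison.

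**Conclusion.** The concern holds. The absence of any stated clustering allowance, and of any calculation for 12 weeks, is plain from the text. At the stated 20% attrition the 80% claim holds only up to an ICC of 0 to about 0.03, the upper end needing 240 enrolled, 20 Peers and the uncorrected pooled formula. At an assumed ICC of 0.05, power is 59% to 75%. For the planned 240 by the t formula at an ICC of 0.10 it is about 55% to 61%. These sizes assume equal numbers per Peer and an ICC range chosen for this review. The statement should be corrected, but the study's conduct and its feasibility purpose are unaffected.

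**What to change.** Replace the power statement with one for the design actually planned: 240 enrolled, 20% attrition (96 per arm), 16 to 20 Peers, and a design effect over a declared ICC range. By the t formula with equal numbers per Peer, power for 20% vs 5% at 6 weeks is 81–83%, 77.5–80.5%, 67–72% and 54.5–61% at ICC 0.01, 0.02, 0.05 and 0.10. These figures are slightly conservative against the simulation. Say that the ICC is assumed and will be estimated from this pilot, which also serves the planning of the later trial. Delete the 12-week sentence, or support it with a stated effect, within-person correlation, ICC and model.

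The cost is wording only: no more participants or Peers and no change of analysis. The stated power becomes less favourable.

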Intervention Procedures: After target enrollment (n=240) is reached, YMCSM Peers will begin the intervention by posting materials according to the timeline developed in the ongoing E-PrEP content project. We will hold weekly project meetings (on different days) with Peers assigned to both E-PrEP and BxNow to ensure appropriate implementation, and to discuss logistical, ethical, or other issues that arise. For participants in the BxNow control arm, Peers will post about general health topics unrelated to HIV or sexual health (e.g. fitness, nutrition, smoking). If a control participant posts a question about PrEP, Peers will refer the individual to the CDC PrEP information site or answer the question privately. Content for both arms will be posted over a 6 week period, and outcome data will be collected via online surveys at baseline, 6, and 12 weeks and after 36 weeks (Table 13). Participants will be given \$20, \$30, and \$40 and 20 online gift-cards or through a Clincard as incentives after completion of assessments at T1, T2, and T3, and T4 respectively.

Anticipated components of E-PrEP: Potential components are listed in Table 2. *However, the exact contents, formats, and mode and timing of delivery of E-PrEP will be informed by input from Peers.*¹²³ We have successfully used this approach in *theSEXword* pilot, with ongoing engagement by participants. We will develop all components for both E-PrEP and the control condition (BxNow), and will also create an intervention activity guide for all 6 weeks, but the exact timeline for intervention delivery will be determined based on findings from Aims 1 and 2. We will thus standardize E-PrEP in its mode of delivery, types of digital media and contents, message framing, and sequence of topics posted and discussed, but Peers will tailor the exact language of posts based on their communication style. Components will be interactive wherever possible; for example, to target a factor such as perceived low risk, participants might assess their risk in an interactive poll, see results in real-time, compare themselves to others, and be engaged by Peers in discussions about risk. To address barriers to access, we might develop a brief time-elapsd video showing where and how to register at a clinic to obtain PrEP. All materials, including assessments, will be smartphone friendly, as most participants use mobile devices.

Table 1. Intervention Timeline

Component	Week	-4	0	6	12	36+
Participant Recruitment						

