Internet. Email addresses will be verified by sending an email to research participants and requiring a verification response via clicking a link to the SM site. To protect false information, participants will provide basic demographic information again when participating in the assessment surveys, and online gift-card incentives that will be provided for completing surveys can only be sent to an email address once and affiliated social media account once for each data collection wave.

4. **Protecting participants from research “posers”:** We will provide research participants with options for verifying the credentials of the researchers and approval of the study through provided contact information of the PI, research assistant, and our local IRB and approval number (phone number, email, institutional website); a signed certificate and SSL (Secure Sockets Layer) for all data transfer over the Internet will be used; participants will be given the option to print the informed consent page for their personal records and receive it via email from the study team.
5. **Monitoring the research participant’s well-being and building trust:** If a participant reveals symptoms of psychological distress via online messaging and/or activity, appropriate referrals and follow-up care and intervention will be made by Peers and/or the research assistant in accordance with a developed resource guide. All efforts will be made to link the online participant to resources at the Adolescent AIDS Program, a Montefiore community health center, or community agency as appropriate. Research participants will be informed of their participation in the study, the duration of the study (12 weeks total) and that all online activity will be observed by peers, the research assistant, and the PI via the online informed consent page. The research assistant will supervise the Peers in documenting and printing all direct messaging and private conversations held with the study social media site members and stored in doubly encrypted files and secure locked filing cabinets in the PI’s office.

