6. **Addressing the lack of in-person communication and possible needs of research participants:** Graphics and video will be used for participants to help overcome limited literacy. Peers will develop profiles and interactive sites in both Spanish and English. The developed resource guide will detail how to remove research participants from the study in the event of an emergency or meeting exclusion criteria. These procedures will include, but are not limited to establishing procedures to facilitate immediate response to each possible risk, calling the police, or contacting an online friend or family member. Participants will be able to directly contact the research team (PI and research assistant) through direct messaging on the social media sites, email, or telephone and this information will be readily accessible on all social media sites used for the study.
7. **Managing confusion among research participants and debriefing:** Peers will remind participants of the on-going research at least once a month throughout the 6-week active intervention period and 6 week post-intervention follow-up period and conduct debriefing over the social media sites. Research participants will have the opportunity to leave comments and ask questions about the online assessments/surveys both before and after completion, and additional contact information of the research team will be made readily available to all participants.
8. **Overcoming Internet limitations of privacy and confidentiality:** An electronic, password protected and encrypted system will be developed to store analyses, and social media activity will remain private to study participants.¹⁶⁴ Research participants will be informed of how communications are recorded and stored during the online informed consent process. Due to the ever-changing and evolving nature of privacy issues on social media sites, we will review privacy settings for all social media study sites at least every four weeks and adjustments will be made to the study sites as necessary.

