Potential Benefits to control condition participants: Participants in BxNow (attention matched control condition) will receive non-overlapping health information about general health topics including physical fitness and nutrition during the 6 week intervention period and linkage-to-care information for comprehensive primary care which would include access to providers who prescribe PrEP. Additionally, they will receive basic information about PrEP and links to further information and local resources at the start of the trial. At the end of the follow-up period (at 12 weeks), after completing the final survey, participants will be given access to all E-PrEP components, information about HIV/STI testing, risk reduction strategies, local resources for sexual health, and information about PrEP. We agree with our current YMCSM Peers and YMCSM community advisory board who advocated for this approach to address issues of *Fairness* and *Justice*, as HIV is a huge burden for this community.

In addition, at the end of the follow-up period (after 12 weeks), both intervention and control groups will be provided again with information about in-person services and we provide direct access to the Adolescent AIDS Program linkage-to-care coordinator and Montefiore Medical Center's primary care linkage-to-care coordinator.

I.7. Risk/benefit ratio. E-PrEP has the potential to increase reach of HIV prevention programs and services, and reduce HIV risk behaviors in YMCSM, but will require pilot testing and refinement. If effective, E-PrEP could be broadly implemented by health centers and community-based organizations, and reduce HIV transmission and promote healthy behaviors. Given the steps that we will take to minimize the chances of breach of confidentiality, participating in this study presents low risk and the risk/benefit ratio is favorable.

I.8 Ethical Principles considered for the online E-PrEP intervention (adapted from Bull et al. 2011)¹⁶⁴

Ethical principles and issues	Issues pertinent to the E-PrEP intervention	How E-PrEP will address the issue

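### The plan says the consent page will state a 12-week study, yet it schedules and pays for a fourth survey (T4) after 36 weeks

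*Combined protocol and SAP*

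**What the plan says.** Section I.5 item 5 lists what participants will learn at consent: "Research participants will be informed of their participation in the study, the duration of the study (12 weeks total". The same sentence adds that online activity will be observed, and it names the vehicle for all of this: "the PI via the online informed consent page".

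The main procedures describe a longer study. Intervention Procedures states that "outcome data will be collected via online surveys at baseline, 6, and 12 weeks and after 36 weeks". The Intervention Timeline has a 36+ column and a T4 row. The Compensation paragraph pays for surveys at "12 weeks(T3), and post 36 weeks (T4"), with $20 for the last. Table 2 (Data Collection) marks one row at 36+: PrEP intention, use, knowledge and attitudes.

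Elsewhere the documents stop at week 12. The reminders that research is in progress run "throughout the 6-week active intervention period and 6 week post-intervention follow-up period" (I.5 item 7). For controls, access to the E-PrEP materials comes as follows: "At the end of the follow-up period (at 12 weeks), after completing the final survey" (I.6).

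**The concern.** A participant told that the study lasts 12 weeks would not expect a survey on PrEP use half a year later. Stating the duration is a basic function of consent, and the plan makes the consent page the place where it is stated. T4 is also the only planned measurement beyond week 12, and it includes PrEP use, a secondary outcome. If the consent page carries the 12-week figure, the consent basis of that wave is open to question, and the question is much easier to settle before T4 than after it.

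The 12-week end is not confined to one phrase. It recurs through the human-subjects sections and appears once in the main procedures, so correcting I.5 item 5 alone would leave the documents in conflict.

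**Working it through.** **The plan's own 12 weeks.** Section I.5 item 7 gives 6 weeks of active intervention and 6 weeks of follow-up: 6 + 6 = 12. The stated duration is therefore reproduced, but only if T3 is the last contact.

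**Where T4 falls.** T4 comes after week 36.

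- Gap beyond the stated end: 36 − 12 = 24 weeks, as a minimum.
- Ratio to the stated duration: 36 / 12 = 3, as a minimum.
- Survey waves within 12 weeks: T1 (week 0), T2 (week 6) and T3 (week 12). Outside: T4, one wave of four.

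**Statements that end the study, or the surveys, at week 12.**

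- Developing BxNow: the trial ends at 12 weeks, after which controls are exposed to all E-PrEP components.
- I.1, summary table: surveys at 0, 6 and 12 weeks. The same rows list four payments ($20, $30, $40, $20), so the table holds both schedules.
- I.2: effectiveness measures come from surveys at 0, 6 and 12 weeks.
- I.4 and I.5 item 11: side-effect questions at each assessment, listed as 0, 6 and 12 weeks.
- I.5 item 5: 12 weeks in total.
- I.5 item 7: 6 + 6 weeks of reminders.
- I.6: final survey and end of follow-up at 12 weeks.
- I.8, Fairness row: end of trial and follow-up at 12 weeks.

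**Statements that keep T4 after 36 weeks.** Intervention Procedures, the Intervention Timeline, Compensation and Table 2. The Data Collection sentence shows leftover editing, with both four and three as the number of time points. The Compensation paragraph before it and the table after it both retain T4, so T4 is a current, planned wave.

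**Is there a bridge between the two?** Nothing in the documents says that participants are told of a longer period, consent separately to T4, or are asked to consent again.

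**Does the sample size depend on T4?** No. The Power Analysis compares 20% with 5% at 6 weeks. With two-sided α = 0.05, 80% power and a continuity correction, the two-proportion formula gives 88 per arm, or 176 in total. Allowing for 20% attrition, 176 / 0.80 = 220, which is the plan's figure. T4 does not enter it.

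**The case against.** The strongest reply is that I.5 item 5 is a stale line. The human-subjects attachment lags the main text in other respects: 16 peers against 16–20, the Bronx against New York, and a different survey platform. Its summary table already includes the fourth payment, so it was partly updated for T4, and the real consent page may have been updated too. The consent form is not available, so this cannot be excluded. If it is so, the remedy shrinks to correcting the protocol text. The contradiction in the current documents remains either way.

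The reply also limits what is at stake. After week 12 the only scheduled participant data collection is one survey on a narrow set of items. Controls receive the E-PrEP components before T4, so T4 is in any case not a comparison with an unexposed control arm.

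A reader might infer more than the documents support:

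- *That participants agreed to only 12 weeks.* The documents show what the plan intends to tell them, not what they read or accepted.
- *That T4 data would be unusable, or response lower.* No section says either, and T4 is paid.
- *That participants would be unaware that the file linking study ID to profile is kept past week 12.* I.2 gives no end date for that file, and the documents do not show what consent says about it.
- *That week 12 is the last linkage-to-care contact, or the date of the debrief.* I.6 does not call the contact final, the Fairness row says staff remain accessible to controls, and I.5 item 7 gives the debrief no date of its own.
- *That two thirds of follow-up lies outside consent.* This counts calendar time, not data collection.

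**Conclusion.** The point holds as an internal inconsistency with a consent consequence, and it should be corrected. As written, the plan tells participants the study lasts 12 weeks and then surveys them at least 24 weeks after that. One of four waves is affected, and the plan applies that wave to all of the 240 planned participants who remain in the study.

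The conclusion rests on two things: the T4 entries in the main procedures are current, which three separate sections support, and the consent page follows I.5 item 5, which cannot be checked here. The 6-week comparison and its sample size are untouched.

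**What to change.** 1. In I.5 item 5, and in the consent text and video, state the actual duration: 36+ weeks and four surveys.
2. Reconcile with T4 the statements on trial end, final survey and 0/6/12-week waves in Developing BxNow, I.1 (summary table), I.2, I.4, I.5 items 7 and 11, I.6 and the Fairness row of I.8. For the side-effect questions, the documents should say whether the listed time points are complete.
3. In I.6, tie control-arm access to E-PrEP materials explicitly to completion of the week-12 (T3) survey, as now planned. If week 12 merely ceases to be called the final survey, the timing of that access becomes ambiguous.
4. For anyone consented on a 12-week statement, show an updated consent screen before the first T4 question.
5. Have the research team send a notice that T4 is coming. Monthly Peer reminders to week 36 would not fit the plan, because Peers are engaged for 9 visits over 7–10 weeks plus two optional follow-up visits.

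The cost is an IRB amendment, revised wording and video, and one added screen, since consent is already an online click-through. A few participants may decline T4. If the consent page proves to describe T4 already, only the protocol text needs to change.
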